9.4. Planned Interim Analyses (If Applicable)

No interim analyses are planned, but electrode impedance will be assessed at each EEG session to decrease the likelihood that degraded signal will be obtained.

9.5. Plans for Coping with Withdrawals and Loss-To-Follow-Up

Given that these are hospitalized inpatients, we anticipate that no more than 20% (two subjects) will fail to complete the study through the inpatient phase (5 EEG sessions). As such, we will recruit 12 subjects in order to obtain 10 completers. In the event that subject discontinuation exceeds our expected limits, we will calculate and display point estimates for as many sessions as the subject completes. Similarly, in the event of unusable EEG data, we will calculate and display point estimates for those sessions with reliable EEG readings.

9.6. Sample Size Rationale

The choice of sample size was based on expert opinion, availability of subjects, and funding limit; we predict that 10 participants may be sufficient for two purposes: 1) to determine the feasibility of obtaining multiple, high quality EEGs during a BRX infusion; and 2) to provide adequate precision for the estimators of variance components and other parameters for which information is needed to plan a future study. With a conservative expected drop-out rate of 20%, we will enroll 12 subjects to attain 10 completers.

10. Safety Monitoring and Management

10.1. Risk / Benefit Assessment

Potential Risks:

(Per informed consent form)

Serious Risks of BRX:

BRX can cause serious side effects, including:

- Excessive sedation and sudden loss of consciousness: BRX may cause subjects to feel very sleepy (excessive sedation) or pass out (loss of consciousness). This is different from normal sleep where one drifts into sleep naturally and can wake up easily. Sudden loss of consciousness (passing out) can occur in some people.
- Because this could cause serious harm, a medical professional will monitor the subject for symptoms of excessive sleepiness every 2 hours while they are awake.
- During the infusion, the subject will be instructed to tell the healthcare provider right away if they feel like they cannot stay awake during the time they are normally awake or if they feel like they are going to pass out. The healthcare provider, under direction of the study doctor, may lower the dose or stop the infusion until the symptoms go away.

- Subjects must have a caregiver or family member with them to help care for the subject's child(ren) during the infusion and to be in the room with the subject if the child(ren) are present during the infusion.

The subject will be directed to tell the healthcare provider if they have any of the following symptoms while getting BRX:

- Feeling more sleepy than usual (they cannot stay awake when they are trying to stay awake)
- Having a hard time paying attention
- Having trouble following simple instructions
- Feeling lightheaded or dizzy or like they are going to pass out

If the subjects start to feel the symptoms listed above, they will be instructed to:

- Tell the healthcare provider right away
- If they are holding a baby, to put their baby down
- Sit or lie down

The healthcare provider and study doctor may decide to stop the infusion. During clinical trials, once BRX was stopped, patients who passed out woke up after a short time. The subject and the study doctor will decide whether to continue BRX.

BRX can cause other serious side effects, including:

- Increased risk of suicidal thoughts or actions. BRX and other antidepressant medicines may increase suicidal thoughts and actions in some people 24 years of age and younger. Depression or other serious mental health illnesses are the most important causes of suicidal thoughts or actions.

Subjects will be advised to monitor suicidal thoughts and behaviors while outpatient in the following manner:

- Pay close attention to any changes, especially sudden changes in mood, behavior, thoughts, or feelings, or if they develop suicidal thoughts or actions.
- Tell the healthcare provider or study doctor right away if they have any new or sudden changes in mood, behavior, thoughts, or feelings during the study.
- Keep all follow-up visits with the subject's regular doctor.
- Contact the study or regular doctor if they have concerns about these symptoms after the infusion has been completed.

Subjects will be instructed to tell the study or regular doctor right away if they have any of the following symptoms, especially if they are new, worse, or worrying the subject:

- attempts to commit suicide and/or harm themselves
- new or worse depression
- other unusual changes in behavior or mood

If the subject has thoughts of harming themselves or others, they will be instructed to go to the nearest emergency department (ED) or call 911. They can also call the National Suicide Prevention Lifeline 24 hours a day at [name].

If there is imminent risk of suicidal behavior at the time of the final safety check (Hour 72 prior to discharge), the subject will be withdrawn from the research study, discharged from the Women's Hospital, and referred to the UNC Emergency Department and/or other appropriate inpatient hospitalization. The study doctor will provide referrals for continued care, which may include hospitalization, but will not be responsible for providing such care following withdrawal from the research study.

Risks Associated with BRX: The following adverse events in the PPD clinical program are considered the most common (more than 1 in 20 people and at least twice the rate of placebo) side effects of brexanolone:

- Sedation (drowsiness) / somnolence (sleepiness)
- Dry mouth
- Passing out (loss of consciousness)
- Flushing of the skin or face (flushing/hot flush)

Other side effects that have occurred in ≥ 2% and > placebo include:

- Faster than normal heart rate (tachycardia)
- Diarrhea
- Upset stomach (dyspepsia)
- Dizziness, feeling faint (presyncope), feeling of losing one's balance (vertigo)
- Mouth and throat pain (oropharyngeal pain)

Two cases of accidental overdosage due to malfunction of the infusion pump were reported (Meltzer-Brody et al, Lancet, 392:1058-1070, 2018). The result was a transient loss of consciousness, with normal consciousness restored within approximately 15 minutes without supportive measures with discontinuation of the infusion. After full resolution of symptoms, both patients subsequently resumed and completed treatment.

Risks Associated with EEG: No medical risks are associated with the EEG. There may be slight discomfort while the electrodes are attached to the scalp, and subjects may not like the smell of the paste or the glue remover. The conductive gel sometimes causes mild scalp irritation. The risk level for adverse impact is minimal.

Risks Associated with Phlebotomy: There may be some discomfort, pain and bruising at the site of needle entry. There is a very small risk of fainting. Infection in the area of the needle insertion is rare. The risk level for adverse impact is low.

Psychological Risks: 1) The structured interview to assess current and lifetime psychiatric illness may be associated with some psychological distress. Some items in the questionnaires may

provoke some negative emotion in some individuals. 2) Additionally, the frequency of administration of mood ratings may prove irritating for some subjects. 3) Subjects may worry about the confidentiality of data collected, including the video samples for processing of emotion in facial expression. Overall, we believe the risk level for adverse impact to be minimal.

Risks to infant children of the subjects as a result of hospitalization and treatment of the mother are mitigated by the requirement of alternative childcare arrangements for the duration of the mother's hospitalization, as outlined in the eligibility criteria of this study. During clinical trials, women were not permitted to breastfeed while receiving brexanolone and for four days following the end of the infusion. Data show that brexanolone is transferred to breastmilk, though the relative infant dose is low (1.3%) and many insurance companies state that breastmilk cannot be used for feedings, in line with the clinical trial criteria. For this reason, we have included the temporary cessation of breastfeeding in the eligibility criteria for this study.

Potential Benefits:

This study is not designed for the benefit of the individuals participating. The primary purpose of this study is to answer research questions. Benefits may accrue, however, as follows: 1) subjects will gain access to what is currently an expensive, effective, approved treatment for PPD; 2) subjects may also benefit by knowing that they are contributing to research aimed at enhancing our understanding of PPD.

10.2. Assessment of Safety

Adequacy of Protection against Risks

Recruitment and Informed Consent:

Subjects will be recruited from inpatients on the UNC PPIU or from the UNC Women's Mood Disorder Clinic. Subjects enrolled in this study will be individuals for whom BRX treatment is the appropriate and recommended course of treatment. Additionally, subjects will be sought from ads seeking volunteers for research on the mechanisms of action of BRX in PPD. For recruitment of women from rural North Carolina, recruitment will be made via contacts with regional gynecologists, county health departments, and through contacts made via the HRSA-sponsored NC Maternal Health MATTERS hotline. Through the NC TraCS Data Access and Informatics Core, we can identify a cohort of UNC Hospital patients for recruitment. UNC uses the EPIC electronic medical record system, which enables communication to potential research participants via email and through the MyChart patient interface. This makes communication with many potential research participants cost effective and highly efficient, because it will enable potential participants to access our online screening tool simply by clicking a link in their email or MyChart electronic message. Additionally, we will capitalize on the TraCS Research Recruitment Service's expertise in enrolling members of communities historically under-represented in research

Trained members of the research team will obtain informed consent from each participant as follows: 1) the subject will have the protocol described; 2) the research assistant will be thoroughly trained in the procedures administered and will, therefore, be able to answer questions that arise. However, if there are unanswered questions, the PI will be available to provide further responses to participants' questions; 3) the subject will sign the consent form, witnessed by the research assistant. A copy of the consent form will be provided to the subject. Subjects will also be consented to access their medical records for information related to relevant medical history. Each will sign a HIPAA authorization form.

Risks Associated with BRX:

The serious risks of BRX include excessive sedation and sudden loss of consciousness. Other risks are described in Section 10.1. These risks will be addressed by the progressive, stepped, infusion rate (with lower doses early), with the dose held rather than increased if the subject experiences dizziness or profound sedation. Patients will be monitored for the duration of the infusion and will also have consistent pulse oximetry to monitor and ensure adequate oxygenation. Additionally, possible side effects of BRX will be monitored with a Likert scale (1=Absent, 2=Mild, 3=Moderate, 4=Severe) that we have used in prior studies of BRX. If the participant reports side-effects of Moderate to Severe intensity, the study coordinator or research assistant will contact the study nurse to determine if adjustment or cessation of the infusion is required.

The UNC Hospitals Arousal Scale (see Table 5). will be administered every 2 hours during planned, non-sleep periods. If a score is equal to 3 on the Arousal Scale, the dose will be reduced by 50% and the inpatient prescriber or psychiatric on-call MD will be notified ([name]). If the score is less than or equal to 2 on the Arousal Scale, the infusion will be discontinued, and the MD will be contacted.

Table 5: UNC Hospitals Arousal Scale

5	Fully awake
4	Arouses easily
3	Arouses with tactile stimuli
2	Arouses to vigorous stimuli
1	Responsive to painful stimuli
0	Unresponsive

Time	Score	Time	Score
Hour 0:		Hour 32:	
Hour 2:		Hour 34:	
Hour 4:		Hour 36:	
Hour 6:		Hour 38:	
Hour 8:		Hour 40:	
Hour 10:		Hour 42:	
Hour 12:		Hour 44:	
Hour 14:		Hour 46:	
Hour 16:		Hour 48:	

Hour 18:		Hour 50:	
Hour 20:		Hour 52:	
Hour 22:		Hour 54:	
Hour 24:		Hour 56:	
Hour 26:		Hour 58:	
Hour 28:		Hour 60:	
Hour 30:			

Risks Associated with EEG: The possibility of rash will be addressed by monitoring the scalp for signs of irritation.

Risks Associated with phlebotomy: Subjects will be seated during the procedure to decrease the risk of fainting, and sterile technique will be employed to decrease the risk, albeit rare, of infection in the area of needle insertion.

Psychological Risks: 1) Structured interview - The risk of discomfort during assessment will be minimized via the use of clinically trained interviewers and highly competent and professional staff. 2) Mood ratings - The risk of irritation with frequency of administration of mood ratings will be addressed by carefully informing potential subjects during the informed consent process about this possibility. In our experience, frequent mood ratings have not resulted in any subject wishing to discontinue the protocol, in part because most subjects in our studies are very dedicated to collecting this information. Subjects will also be informed of their right to withdraw from the study at any time. 3) Multiple measures will be undertaken to ensure the confidentiality and integrity of the data obtained, including clinical information, mood ratings and video samples. All data collected for analysis in this study will be de-identified at collection and will stay on encrypted, password-protected computers. Only the PI and the study coordinator will have access to individually identifiable patient information. Each subject will receive a code number, and the code will be stored - separately from data collected - in a locked file the Study Coordinator's locked office. Additionally, the video samples will be obtained on a dedicated, encrypted, password protected laptop, which will be returned after use and stored in a locked filing cabinet in the Study Coordinator's locked office.

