The Pharmacist or designee will be responsible for preparing study drug for subject dosing. The prepared admixture will be administered at room temperature.

Refer to the Pharmacy Manual for specific instructions regarding requirements for IV bags and labeling, infusion sets, infusion preparation and administration instructions.

This is an open-label study. Subjects will receive a 60-hour continuous IV infusion of brexanolone.

The specific infusion dose of study drug will be calculated based on weight (obtained at screening) for each subject and administered according to the dose regimen in Table 2.

Table 2: Infusion Rate

Time point	Day 1 0 to 4 hours	Day 1 4 to 24 hours	Day 2 to 3 24 to 52 hours	Day 3 52 to 56 hours	Day 3 56 to 60 hours
Dose	30 mcg/kg/hour	60 mcg/kg/hr	90 mcg/kg/hr	60 mcg/kg/hr	30 mcg/kg/hr

Dosing will begin in the morning (on Day 1) to avoid the dose increase to 90 mcg/kg/hour late in the day and to avoid awakening subjects during the night for completion of study assessments.

Refer to the Pharmacy Manual for complete details on preparation and administration.

The pharmacist or designee for drug accountability is to document the date and time of preparation of test article and for which subject the study drug was intended (i.e., record subject initials and birth date or another unique identifier).

At the end of the study, any unused study drug will be destroyed locally per the site's procedures; disposition of study drug will be documented.

Modification:

If the UNC Hospitals Arousal Score = 3 (see Table 5), the dose will be reduced by 50% and the doctor will be contacted. If there are mild symptoms (e.g., dizzy, lightheaded), the dose will be held at the current rate rather than increased. Typically, these mild symptoms will resolve with more time at the lower infusion rate, and then subjects can tolerate an increase up to 90mcg/kg. The infusion will be immediately stopped if there is loss of consciousness, or if the UNC Hospitals Arousal Scale score is less than or equal to 2, or if pulse oximetry reveals hypoxia (oxygen saturation below 90%).

For patients who do not tolerate the 90 mcg/kg/hour dose, a reduction to 60 mcg/kg/hour may be considered during the time that the 90 mcg/kg/hour is scheduled to occur.

If other intolerable adverse events occur, the infusion will be stopped until the symptoms resolve. The infusion may be resumed at the same or lower dose as clinically appropriate.

Accountability:

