Subjects will be monitored for hypoxia throughout intervention phase using continuous pulse oximetry equipped with an alarm. Oxygen saturation need only be recorded in the event of hypoxia, in which case, the event is to be recorded as an AE. The infusion will be immediately stopped if pulse oximetry reveals hypoxia. After an episode of hypoxia, the infusion should not be resumed.

Monitoring for Excessive Sedation and Loss of Consciousness

For the duration of the infusion, subjects must be assessed for excessive sedation and loss of consciousness by a healthcare provider every 2 hours during planned, non-sleep periods. If excessive sedation or loss of consciousness occurs at any time during the infusion, the infusion will be stopped until the symptoms resolve. The infusion may be resumed at the same or lower dose as clinically appropriate (see Section 6.1), and an AE is to be recorded.

Vital Signs

Vital signs include oral temperature (°C), respiratory rate, heart rate, and blood pressure. Heart rate and blood pressure to be collected in supine position at all scheduled time points as well as in the standing position at specific time points listed in Table 3.

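### Section 10.2 holds the dose for profound sedation, where section 6.1 halves or stops it; the section 7.4 stop for excessive sedation has no arousal score

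*Combined protocol and SAP*

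**What the plan says.** Four sections tell staff what to do when a woman becomes sedated.

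- **Section 6.1 (Modification)** sets graded actions. For the mildest level: "If there are mild symptoms (e.g., dizzy, lightheaded), the dose will be held at the current rate rather than increased". For the next: "If the UNC Hospitals Arousal Score = 3 (see Table 5), the dose will be reduced by 50" per cent, with a call to the doctor. For the most severe: "The infusion will be immediately stopped if there is loss of consciousness, or if the UNC Hospitals Arousal Scale score" is 2 or lower; low oxygen saturation is also a stop trigger. It adds: "If other intolerable adverse events occur, the infusion will be stopped until the symptoms resolve", after which the infusion may restart at the same or a lower dose.
- **Section 7.4 (safety monitoring)** uses words instead of scores: "If excessive sedation or loss of consciousness occurs at any time during the infusion, the infusion will be stopped until the symptoms resolve". It then allows a restart, citing 6.1, with one exclusion: "After an episode of hypoxia, the infusion should not be resumed".
- **Section 10.1** describes excessive sedation in lay terms and lets the provider, directed by the study doctor, lower the dose or stop. Holding is not mentioned.
- **Section 10.2** says the risk is handled by stepping the rate up, "with the dose held rather than increased if the subject experiences dizziness or profound sedation". Its next paragraph gives the score rules: halve and notify at 3, discontinue and call at 2 or lower.

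Section 6.6 allows no dose adjustments beyond those in 6.1. Table 5 labels scores 0 to 5 by how easily the woman is roused; it uses neither *excessive* nor *profound* sedation.

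**The concern.** Excessive sedation and sudden loss of consciousness are the first serious risk listed in 10.1. The hold clause in 10.2 pairs dizziness, which 6.1 treats as mild, with profound sedation, which cannot plausibly be mild. For the second of these it names too weak an action.

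The trigger in 7.4 raises a smaller, separate problem. Excessive sedation is tied to no score, yet the operative rules elsewhere are scored. A woman who rouses only to touch (score 3) and whom staff regard as excessively sedated falls under two different instructions.

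Wording matters here because the Arousal Scale is given every two hours in planned waking periods, while the 7.4 rule applies at any time. Between scheduled checks, staff may be acting on the words. What is at stake is the infusion rate a sedated woman receives; no sample size or analysis is affected.

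**Working it through.** The plan states no figure to reproduce. The check sets the rules side by side and converts the differences into infusion rates.

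**Step 1. Actions by level of sedation**

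| Situation | 6.1 | 10.2, hold clause | 10.2, score paragraph | 7.4 |
|---|---|---|---|---|
| Mild symptoms | Hold | Hold (dizziness) | Not addressed | Not addressed |
| Score 3 | Halve, contact doctor | Hold, if this is profound sedation | Halve, notify doctor | Stop, if this is excessive sedation |
| Score 2 or lower | Stop | Hold, if this is profound sedation | Discontinue, contact doctor | Stop, if this is excessive sedation |
| Loss of consciousness | Stop | Not addressed | Not named | Stop, restart possible |

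The two sets of score rules (6.1 and the score paragraph of 10.2) agree on the immediate action. The hold clause agrees with them only if profound sedation means score 4 (easily roused) or 5 (fully awake), which is not a credible reading.

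**Step 2. Rates if the hold clause alone were followed**

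Inputs: the schedule in 4.1 and Table 2 has two increases, 30 to 60 mcg/kg/hour at Hour 4 and 60 to 90 at Hour 24. Assumptions: profound sedation means score 3 or lower, and halving applies to the rate then running.

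- Hour 24: hold = 60; score 3 = 0.5 × 60 = 30; score 2 or lower = 0. The hold is 60 − 30 = 30 or 60 − 0 = 60 mcg/kg/hour above 6.1.
- Hour 4: hold = 30; score 3 = 0.5 × 30 = 15; score 2 or lower = 0. The hold is 30 − 15 = 15 or 30 − 0 = 30 mcg/kg/hour above 6.1.

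**Step 3. Score 3 regarded as excessive sedation**

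- At the 30 step: 0.5 × 30 = 15 under 6.1 and 10.2, against 0 under 7.4.
- At the 60 step: 0.5 × 60 = 30, against 0.
- At the 90 step: 0.5 × 90 = 45, against 0.

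**Step 4. Frequency**

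The documents give no rate for either situation, so none is estimated.

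**The case against.** The best defence is that the hold clause is part of a narrative overview and the operative rules follow in the next paragraph. Not increasing the rate does not forbid reducing or stopping it. Section 6.6 makes 6.1 the governing text, arousal is scored every two hours, oximetry is continuous, and a score of 3 already brings in a doctor, who under 10.1 may stop the infusion. Halving first and then stopping on medical judgement is a workable sequence. Section 6.3 adds that nurses know the regimen and prescribers are REMS-certified. All of this stands, and it makes a wrong action unlikely. It does not make the clause correct: a safety section should not pair profound sedation with the response meant for dizziness.

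Four stronger readings are tempting and are not supported.

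- A reader might infer that 6.1 expressly restricts holding to mild symptoms. It does not; mild symptoms are simply the trigger it gives.
- A reader might infer that the hold clause can matter at the two scheduled increases and never afterwards. Section 6.1 expects a held woman to step up later once symptoms settle, so the clause could apply then too.
- A reader might infer that restart after loss of consciousness is left open, depending on which section is read. Section 7.4 permits it except after hypoxia, and 10.1 leaves continuation to the woman and the study doctor. What remains is one word, *discontinued*, for score 2 or lower in 10.2.
- A reader might infer that counts of adverse events of special interest at score 3 are distorted. A sedation-related dose reduction already qualifies under 10.3, so a halving is captured either way.

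**Conclusion.** The inconsistency is real and should be corrected, but it is a wording fault in a plan whose score rules agree. Taken alone, the hold clause would leave a profoundly sedated woman at 60 mcg/kg/hour at Hour 24 where 6.1 gives 30 or 0, or at 30 at Hour 4 where 6.1 gives 15 or 0. A score of 3 regarded as excessive sedation gives 15, 30 or 45 mcg/kg/hour under 6.1 and 10.2, against 0 under 7.4. The first comparison depends on reading profound sedation as score 3 or lower, the second on clinical judgement that a score of 3 is excessive, and both on halving the rate then running. The documents do not support a claim that mis-dosing is expected.

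**What to change.** 1. In 10.2, delete the words *or profound sedation* from the hold clause, so that holding applies to mild symptoms, as in 6.1.
2. In 7.4, keep the stop for excessive sedation or loss of consciousness and add the 6.1 score actions as the minimum response. At score 3, at least halve and call the doctor, who may stop; at score 2 or lower, stop. The clinical-judgement stop should stay, because replacing it with scores alone could narrow a safety rule.
3. In 10.2, change *discontinued* at score 2 or lower to *stopped*, with resumption as in 7.4 and 10.1 and none after hypoxia.

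The cost is a wording amendment and brief retraining of the infusion staff. No patients or procedures are added.
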